6 STUDY SCHEMA

7 SUBJECT ELIGIBILITY

All patients seeking treatment for cancer metastatic to the brain from an extracranial primary site with a contrast-enhanced MRI scan showing 4 or more brain metastases at the Duke Comprehensive Cancer Center will be considered.

7.1 Inclusion Criteria

1. A contrast-enhanced MRI scan showing ≥ 4 treatable brain metastases.
2. Age ≥ 18 years of age.
3. KPS ≥ 70
4. Patient must be GPA score 0.5 or greater (See Appendix A)
5. Life expectancy of at least 3 months
6. Postoperative patients with resected brain metastases are eligible.
7. Largest lesion ≤ 4 cm diameter
8. Must be a candidate for MRI imaging
9. Previous cranial SRS/WBRT is allowed if > 3 months prior to SIMT
10. Must be capable of providing informed consent.
11. Women of childbearing age must have a negative serum pregnancy test to meet eligibility per Duke policy.

7.2 Exclusion Criteria

1. Primary lesions with the following histologies: small cell carcinoma, germ-cell tumors, lymphoma, leukemia, and multiple myeloma.
2. Metastases within 2 mm of the optic apparatus
3. Patients who are unable to obtain MRI
4. Evidence of leptomeningeal disease.
5. Greater than 10 brain metastases; excluding previously treated and stable brain metastases.
6. Pregnant women are excluded.

8 INVESTIGATIONAL PLAN

8.1 Study Design

This prospective study of 40 patients will assess the efficacy of SIMT SRS for multiple brain metastases. Dosimetric data, treatment delivery endpoints, clinical outcomes including local control, distant failure and quality of life will be assessed through this trial.

8.1.1 Dose Modification

Radiation doses will be adjusted as described below in Section 9

8.1.2 Safety Considerations

Patients will be evaluated throughout the study for toxicity. Patients will be assessed for all adverse events during treatment and post completion of SRS. Adverse events will be considered to be any grade 3, 4, or 5 event that is deemed by the PI to be probably, possibly, or definitely related to the SRS treatment. Acute adverse events will be collected at the first post-SRS visit. This visit will occur approximately 4 weeks after the last fraction of SRS is

delivered. These will be collected and reported. In our experience, SRS treatment side effects are rare and are solely neurologic.

In light of previous observations, it may be that increasing the treatment volume may also come with a potential cost of increased morbidity.

8.1.3 Treatment Interruptions during RT

There will be no need for treatment interruptions as most treatments will be a single treatment. Some patients will require five treatments on business days (refer to section 9.3) and in our experience, patients are able to complete all five treatments without interruption. Patients can start their treatment any day of the week and weekend breaks are permitted as long as patients have their treatments on consecutive business days. They will be evaluated daily by radiation therapists and if a treatment interruption occurs, as long as medically stable as deemed by the treating physician, patients will continue treatment until completion. If a treatment interruption occurs but the patient completes all five treatments within 10 business days, then this would not be considered a protocol deviation.

8.1.4 Concomitant Medications/Therapies

Symptomatic patients should be placed on dexamethasone at the time of brain metastasis diagnosis at the discretion of the treating radiation oncologist. The drug may be administered orally or intravenously and the dose adjusted throughout the course of treatment. In patients who cannot tolerate taper and/or cessation of steroids, the steroid dose will be maintained at the lowest dose consistent with good medical practice.

8.1.5 Randomization

There will be no randomization.

8.2 Rationale for Selection of Dose, Regimen, and Treatment Duration

Doses for radiosurgery are derived from the RTOG 90-05 study, which calculated the maximum tolerated dose for brain metastases as a function of size.¹⁸ We also found that for large lesions in our study of SRS for GBM that this fractionation was well tolerated¹⁹ as it would certainly reduce the biologically effective dose likely leading to RN.

8.3 Rationale for Correlative Studies

Not applicable.

8.4 Definition of Evaluable Subjects, On Study, and End of Study

All patients who receive SIMT SRS will be included in analyses.

8.5 Early Study Termination

This study can be terminated at any time for any reason by the PI-sponsor. If this occurs, all subjects on study should be notified as soon as possible. Additional procedures and/or follow up should occur in accordance with Section 10.7, which describes procedures and process for prematurely withdrawn patients.

9 RADIATION THERAPY

9.1 Type, Classification, Location, and Short Description

SRS will be performed in the Department of Radiation Oncology, Duke University Medical Center. The gross tumor volume will be delineated by [name] MD PhD, [name] PhD, or [name] PhD, and radiosurgery planning will be assisted by board-certified Physicists. Patients will be treated following the RTOG Stereotactic Radiotherapy Guidelines (Appendix B), available at <http://dx.doi.org/10.1016/j.prro.2011.06.014>

9.2 Equipment

SRS doses will be delivered as described below with a linear accelerator-based Novalis Tx and TrueBeam STX system, following established procedures for image guided stereotactic radiosurgery. Both systems are high-energy linear accelerators from Varian Medical Systems utilizing the same model of a high-definition collimator (2.5mm leaf thickness at isocenter) to precisely shape the radiation beam. Both units use kilovoltage orthogonal x-ray imaging systems and cone-beam CT to ensure the patient is set-up in the exact, correct position with each and every treatment. While the system names are different, the Novalis Tx and TrueBeam STx yield equivalent dose distributions.²⁰

9.3 Dose Specifications

The total dose is dependent on the maximum diameter of the PTV and total lesion volume as described below:

Maximum PTV Diameter	Assigned Dose
< 2.0 cm	20 Gy x 1
2.0-3.0 cm	18 Gy x 1
≥ 3cm	5 Gy x 5

The total prescribed dose is determined by tumor size. These assigned doses may be decreased based on clinical judgment. V12 will be recorded for each case. V12 is defined as the volume of normal brain receiving 12 Gy. Normal brain is defined as volume of normal brain parenchyma (not including normal tissue outside of meninges), minus total PTV volume.

If V_{12Gy} (Volume receiving 12 Gy) for normal brain parenchyma (i.e., excluding the PTV's) exceeds 20 mL, then the dose to all lesions will be 5 x 5 Gy where one treatment will be delivered each day for five consecutive business days (i.e. the first treatment may start mid-week and be completed in the following week). If there is a lesion in the brainstem, all lesions will be treated with 5 Gy x 5 because the brainstem is particularly sensitive to high doses of radiation given in a single fraction.

The SRS dose has been selected in order to provide a high rate of local control with minimum risk of radionecrosis. These doses are already being used in our clinic as our departmental standard of care derived from the RTOG 9005 SRS dose escalation study.¹⁸

The dose will be prescribed to the absolute isodose surface, which encompasses the margin of the metastasis, as defined by the contrast-enhanced MRI. The maximum dose, minimum dose to the GTV and PTV, and percent volume coverage of the GTV and PTV will be recorded for each patient. The

prescription dose shall be delivered to the absolute isodose surface. The minimum dose shall be established by the SRS treatment planning software and/or by the target dose-volume histogram.

Each lesion will be prescribed an SRS dose according to the maximum diameter of the PTV as well as the total volume. If any two lesions are within 1 cm of one another, the prescription dose to these groups of lesions will be based on the maximum diameter across these two lesions. At the discretion of the PI, the dose to lesions in eloquent areas of the brain (e.g., the motor strip or the speech center) may be reduced from 20 to 18 Gy for PTV \leq 2cm in diameter and from 18 to 16 Gy for PTV 2-3cm diameter.

To summarize, lesions will be treated in one fraction unless a lesion is greater than 3cm, located in the brainstem, or the V12 of the normal brain exceeds 20 cc.

In the setting of multiple metastases, a lesion(s) may need to be resected because of large size or mass effect that causes serious neurologic deficits. The resulting resection cavity/cavities can be treated along with the other unresected metastases with the SIMT technique. This has not occurred commonly in our practice but surgery does not preclude the use of this technology.

Isodose distributions must be calculated, and the prescription isodose line clearly designated, for each target lesion in the transverse, coronal, and sagittal planes. The isodose distributions on the required three planes for each target lesion will include isodose lines (in % dose) that represent 20% dose increments. Cumulative dose-volume histograms must be calculated for all target lesions, as well as the brainstem, optic chiasm, optic nerves, eyes and normal brain parenchyma.

Each lesion will be consistently labeled according to institutional protocol and separately followed and documented. With every MRI, any changes in each lesion will be recorded. MRI image registration using department radiation planning software (iPlan) will aid in detecting differences in lesion size and number.

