9.9 Quality Assurance of Dose Distribution

Lesion Identification

Lesions must be uniquely identified by anatomical location, e.g., medial left frontal lobe, inferior/superior right cerebellum, etc, so that these lesions can be readily followed on serial MRI's.

Isodose QA

Four isodose lines should be reviewed: The prescription isodose line, 90% of the prescription isodose line (not 90% of total dose), 80% of the prescription isodose line, and 50% of the prescription isodose line.

Target Coverage QA

Per protocol: The submitted 100% isodose line (100% of the prescription dose, not maximum dose) covers >99% of the target volume.

Acceptable variation: 100% isodose line covers >95% of the target.

Unacceptable deviation: 100% isodose line covers >90% of the target.

Dose QA

Per protocol: If the maximum dimension of the tumor is:

< 2.0 cm: 20 Gy

≥ 2.0 cm and < 3.0 cm: 18 Gy

≥3.0 cm: 5 Gy x 5 all lesions, regardless of diameter

In addition, if any lesion is located in the brainstem or the total V_{12Gy} calculated for single-fraction treatment exceeds 20 ml, all lesions will be treated with 5Gy x 5, regardless of diameter. For metastases that are close to critical structures, doses will be reduced as stated above in Section 9.3.

Unacceptable deviation: Anything else

Dose Conformity QA

The ratio of prescription isodose volume (for maximum planned prescription dose per plan) to the total target volume (*Conformity Index*) is:

Per protocol if between 1.0 and 2.0

Acceptable variation if ≥ 0.9 but < 1.0 or >2.0 but ≤ 3.5 .

Unacceptable deviation if > 3.5 .

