10.3 Treatment Period

Treatment will range from 1 to 5 consecutive business days and those patients that get multiple treatments will be observed every day by radiation therapists.

Those patients that will be treated in 5 days are the following:

- 1) at least 1 metastasis > 3cm
- 2) V12 > 20 cc for normal brain parenchyma, all lesions will receive 5 Gy x 5
- 3) If there is a brainstem lesion

If a treatment interruption occurs but the patient completes all five treatments within 10 business days, then this would not be considered a protocol deviation.

Sexually active, subjects must agree to use appropriate contraceptive measures for the duration of the study treatment (i.e. from SRS CT simulation to the completion of SRS treatment, which is approximately 1-2 weeks).

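### The 1 cm lesion-pair dosing rule in 9.3 is undefined and missing from the 9.3 summary, 10.3 and the 9.9 Dose QA, so a plan that follows 9.3 can be scored an unacceptable deviation

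*Combined protocol and SAP*

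**What the plan says.** Section 9.3 ties dose to size: "The total dose is dependent on the maximum diameter of the PTV and total lesion volume as described below". Its table gives 20 Gy x 1 below 2.0 cm, 18 Gy x 1 from 2.0 to 3.0 cm, and 5 Gy x 5 from 3 cm upward. A brainstem lesion, or a normal-brain V12 above 20 mL, moves every lesion to 5 Gy x 5. The section then adds a rule for neighbours: "If any two lesions are within 1 cm of one another", then "the prescription dose to these groups of lesions will be based on the maximum diameter across these two lesions". It also permits lower doses in two ways. One is general: "These assigned doses may be decreased based on clinical judgment". The other is a PI-discretion step down for lesions in eloquent areas (20 to 18 Gy, or 18 to 16 Gy).

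Three places restate when a patient gets one fraction or five, or what dose counts as correct:

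- **9.3, summary paragraph:** "lesions will be treated in one fraction unless a lesion is greater than 3cm, located in the brainstem", or V12 above 20 cc.
- **10.3:** "Those patients that will be treated in 5 days are the following", followed by three groups: a metastasis above 3 cm, V12 above 20 cc, a brainstem lesion.
- **9.9, Dose QA:** bands set by the largest dimension of the tumor, with the band from 3.0 cm extending 5 Gy x 5 to every lesion; then the brainstem and V12 triggers; then "For metastases that are close to critical structures, doses will be reduced as stated above in Section 9.3"; and finally "Unacceptable deviation: Anything else".

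None of the three mentions neighbouring lesions.

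**The concern.** The pair rule is worded as mandatory and it acts through bands that change both dose and number of fractions. A planner who works from 9.3 and a QA reviewer who works from 9.9 can therefore reach different answers for the same two lesions, and the planner's answer is then recorded as unacceptable. Two planners in the department could also differ, because the protocol does not say what is measured across the pair.

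At stake are the treatment actually given, the count of dose deviations, and the interpretation of local recurrence (key secondary) and radionecrosis (exploratory), both of which plausibly depend on dose and fractionation. Section 10.7.1 lists protocol deviation among the possible reasons for PI-initiated withdrawal, although the documents do not say that an unacceptable QA score counts as one.

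**Working it through.** The plan gives no figure to reproduce here. The check sets the rules side by side and applies the 9.3 bands to example pairs.

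**Inputs from the documents.** Bands: below 2.0 cm, 20 Gy x 1; 2.0 to 3.0 cm, 18 Gy x 1; from 3 cm, 5 Gy x 5 (9.3, and in substance 9.9). Pair trigger: 1 cm or less (9.3). PTV = GTV plus 1 mm in every direction (9.6).

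**Assumptions.** Spherical PTVs of diameters d1 and d2, edge-to-edge gap g of at most 1 cm, no brainstem lesion, V12 at or below 20 mL, and no single lesion of 3 cm or more.

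**Reading A, joint span:** D = d1 + g + d2.

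| d1, d2, g (cm) | D (cm) | 9.3 pair rule | 9.9, lesion by lesion |
|---|---|---|---|
| 1.2, 1.2, 0.8 | 3.2 | 5 Gy x 5 | 20 Gy x 1 for each |
| 0.8, 0.8, 0.5 | 2.1 | 18 Gy x 1 | 20 Gy x 1 for each |
| 1.5, 2.5, 0.5 | 4.5 | 5 Gy x 5 | 20 Gy x 1 and 18 Gy x 1 |
| 0.6, 0.6, 0.5 | 1.7 | 20 Gy x 1 | 20 Gy x 1 for each |

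In the first and third rows the 9.3 summary and 10.3 also give one fraction, since neither lesion exceeds 3 cm. The last row shows that some pairs raise no conflict.

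**Reading B, larger single diameter:** D = max(d1, d2). If both lesions are below 3 cm, D is below 3 cm, so the rule can never move a pair to five fractions. A conflict remains only when the two lie in different bands. For 1.5 and 2.5 cm, D = 2.5 cm, so 9.3 gives 18 Gy to both, while 9.9 expects 20 Gy for the 1.5 cm lesion.

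**PTV or tumor.** Section 9.3 measures the PTV and 9.9 the tumor. The expansion adds 0.2 cm to a diameter, so PTVs of 1.2, 1.5 and 2.5 cm correspond to tumors of 1.0, 1.3 and 2.3 cm. The bands are the same, so this difference does not create the conflict in these examples.

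**How often.** The documents give no distribution of lesion size or spacing. For equal PTVs of diameter d, the largest joint span a flagged pair can have is 2d + 1 cm. With d below 1.0 cm this is below 3 cm, so no pair reaches the five-fraction band. As an illustration only, a simulation placed equal, non-overlapping spheres at random in a 1300 mL sphere, with 4,000 patients per setting:

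| At least one pair within 1 cm and | 4 lesions | 6 lesions | 10 lesions |
|---|---|---|---|
| PTV 1.2 cm: any span | 13% | 31% | 66% |
| PTV 1.2 cm: span of 3 cm or more | 7% | 17% | 42% |
| PTV 0.8 cm: span of 2 cm or more | 6% | 15% | 40% |

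These figures use Reading A and do not remove patients already on 5 Gy x 5 for another reason.

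**Permitted reductions.** Section 9.3 allows a decrease on clinical judgment for any lesion. The Dose QA recognises only reductions near critical structures, so a decrease made for another reason falls into its residual category. Section 9.3 does not use the term critical structures; it names eloquent areas and the brainstem.

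**The case against.** A summary paragraph and a description of the treatment period need not repeat every sizing convention, so their silence may be incompleteness and not a rival dose rule. That is fair for the 9.3 summary and 10.3 taken alone. It does not help 9.9, which is a scoring rule with a closed residual category.

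One could also treat the pair as the tumor that 9.9 measures, which would remove the conflict under Reading A. Nothing in 9.9 says so, and both 9.3 and 9.9 require lesions to be identified and followed individually.

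A reader might infer that the protocol leaves a patient's other lesions unaddressed once a pair reaches five fractions. The documents do not support that fully: 9.9 extends 5 Gy x 5 to every lesion in the top band, and 10.3 assigns five days by patient. What is unstated is whether this holds when a pair, not a single lesion, reaches that band, since the pair rule in 9.3 speaks only of the grouped lesions.

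A reader might also infer that the critical-structures reference points to nothing. It has a target of sorts: 9.3 has a brainstem rule and a general allowance, and 9.7 sets limits for the brainstem, optic chiasm and optic nerves. The mismatch is one of wording and scope.

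Finally, no decision rule uses the Dose QA score, all treated patients are analysed (13.1), and local recurrence and radionecrosis are descriptive. That stands and limits the consequences.

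**Conclusion.** The inconsistency holds. Section 9.3 contains a dosing rule that three other places omit, its key quantity is undefined, and under either reading a plan that follows 9.3 can be scored as an unacceptable deviation. The Dose QA also fails to recognise the clinical-judgment decrease that 9.3 allows.

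The size depends on the reading. Five fractions versus one requires the joint span, which is the more natural sense of the phrase and the only one under which the rule can change fractionation. It would go too far to say that every close pair is caught between five fractions and one: under the larger-diameter reading the gap is 18 versus 20 Gy for the smaller lesion only. No conflict arises in patients already on 5 Gy x 5 for V12, brainstem or a lesion of 3 cm or more.

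Two further inferences are not supported. Treatment cannot differ between sites, because 9.1 places all SRS in one department; the variation is between planners. And the simulated percentages are not estimates for this trial, because lesion size and placement were assumed; lesion count alone does not establish how close the lesions lie.

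The primary survival analysis is not directly affected. Treatment given, deviation counts and the descriptive local-recurrence and radionecrosis results are. The point should be corrected, and the correction is cheap.

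**What to change.** - Reconcile 9.3, its summary paragraph, 10.3 and the Dose QA in 9.9 so that all give one dose and fractionation for the same pair.
- Define the pair's diameter as a single measurable quantity.
- State whether the extension of 5 Gy x 5 to every lesion in 9.9 applies when a pair, and not a single lesion, reaches the five-fraction band.
- Make the Dose QA categories agree with the dose reductions the protocol permits, and make the cross-reference to 9.3 match the terms 9.3 uses.

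The sponsor decides which rule governs; no dose or rule is proposed here. The cost is wording in 9.3, 10.3 and 9.9 and on the QA form. Some plans may need rescoring. No new procedure is needed.

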9.4 Localization, Simulation, and Immobilization

An FDA-approved stereotactic radiosurgery system will be used for all localization and treatment planning. All patients must undergo a pretreatment contrast-enhanced planning MRI within one week prior to radiosurgery. Patients who have completed a diagnostic MRI with contrast within 14 days of radiosurgery do not need to have a planning MRI. All patients will be treated on the Varian/BrainLAB linear accelerator-based radiosurgery system (Novalis Tx & TrueBeam STX) following established QA procedures for treatment delivery.

Per the standard of care, target volume and isocenter determination will be based on a contrast-enhanced axial MRI scan. A CT scan will be performed with the patient's head immobilized in a custom thermoplastic mask, and the CT and contrast-enhanced axial 3D MR images fused. The MRI study used to plan the radiosurgical treatment must be the same as used to determine the size of the metastatic lesions. The MRI slice thickness may not exceed 1 mm. The target volume will include the enhancing portion of the metastatic lesion. Surrounding areas of edema will not be considered part of the target volume.

9.5 Imaging

Orthogonal KV and CBCT imaging of patient in the immobilization mask will be done before each radiation delivery.

9.6 Treatment Planning/Target Volumes

Target Volume Definitions

The volumes shall be defined by contrast-enhanced MRI with the patient in the treatment position. ICRU-50 nomenclature target volumes are defined as follows: GTV: Defined as contrast-enhancing tumor seen on pretreatment MRI. PTV: For the purpose of this study, the PTV is defined as the GTV uniformly expanded by 1 mm in all dimensions. The PTV must be ≤ 4.0 cm.

Target Dose

Prescription Specification: The dose should be prescribed to the highest isodose line encompassing the PTV.

Dose Definition

Dose is specified in Gray (Gy).

9.7 Dose Limitations for Normal Tissue

The treatment parameters should be modified to optimize the conformity of the prescription volume to the target volume while minimizing dose to critical structures. In patients receiving single fraction treatments, the maximum point dose to the optic chiasm and optic nerves should not exceed 10 Gy and maximum dose to the brainstem should be less than 12.5 Gy. In patients receiving 5 Gy per fraction for five fractions, the maximum point dose to the optic chiasm and optic nerves should not exceed 20 Gy and the maximum dose to 99% of the brainstem should not exceed 26 Gy.

9.8 Treatment Verification

Patients will be monitored by the treating physician ([name], [name], or [name]), and the therapists and physicists during the procedure. The departmental policy has been standard of care time out prior to delivery of each fraction of radiation therapy and this will be meticulously adhered to.

9.9 Quality Assurance of Dose Distribution

Lesion Identification

Lesions must be uniquely identified by anatomical location, e.g., medial left frontal lobe, inferior/superior right cerebellum, etc, so that these lesions can be readily followed on serial MRI's.

Isodose QA

Four isodose lines should be reviewed: The prescription isodose line, 90% of the prescription isodose line (not 90% of total dose), 80% of the prescription isodose line, and 50% of the prescription isodose line.

Target Coverage QA

Per protocol: The submitted 100% isodose line (100% of the prescription dose, not maximum dose) covers >99% of the target volume.

Acceptable variation: 100% isodose line covers >95% of the target.

Unacceptable deviation: 100% isodose line covers >90% of the target.

Dose QA

Per protocol: If the maximum dimension of the tumor is:

< 2.0 cm: 20 Gy

≥ 2.0 cm and < 3.0 cm: 18 Gy

≥3.0 cm: 5 Gy x 5 all lesions, regardless of diameter

In addition, if any lesion is located in the brainstem or the total V_{12Gy} calculated for single-fraction treatment exceeds 20 ml, all lesions will be treated with 5Gy x 5, regardless of diameter. For metastases that are close to critical structures, doses will be reduced as stated above in Section 9.3.

Unacceptable deviation: Anything else

Dose Conformity QA

The ratio of prescription isodose volume (for maximum planned prescription dose per plan) to the total target volume (*Conformity Index*) is:

Per protocol if between 1.0 and 2.0

Acceptable variation if ≥ 0.9 but < 1.0 or >2.0 but ≤ 3.5 .

Unacceptable deviation if > 3.5 .

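### Protocol sections 9.3, 9.9 and 10.3 give dose-band and QA rules that conflict however *tumor* is read, and the eligibility and PTV size limits do not line up

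*Combined protocol and SAP*

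**What the plan says.** **Prescribing (protocol 9.3).** The opening sentence reads "The total dose is dependent on the maximum diameter of the PTV and total lesion volume as described below". The table has three rows by PTV diameter: below 2.0 cm (20 Gy x 1), 2.0-3.0 cm (18 Gy x 1), and 3 cm or more (5 Gy x 5). I call these the first, middle and last rows. The section then adds:

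- "The total prescribed dose is determined by tumor size";
- "Each lesion will be prescribed an SRS dose according to the maximum diameter of the PTV as well as the total volume";
- for two lesions within 1 cm, "the prescription dose to these groups of lesions will be based on the maximum diameter across these two lesions";
- "These assigned doses may be decreased based on clinical judgment";
- a permitted reduction in eloquent areas, from 20 to 18 Gy for a PTV of 2 cm or less and from 18 to 16 Gy for one of 2-3 cm;
- five fractions to all lesions if there is a brainstem lesion or if V12 exceeds 20 mL.

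The closing summary of 9.3 puts the size trigger for fractionation strictly above 3 cm. Section 10.3 does the same, for patients with at least one such metastasis.

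**Scoring (protocol 9.9).** The Dose QA begins "Per protocol: If the maximum dimension of the tumor is" and lists below 2.0 cm, 2.0 to below 3.0 cm, and 3.0 cm or more. In the last band every lesion goes on 5 Gy x 5 whatever its own size. It refers to 9.3 for reductions near critical structures, then closes with "Unacceptable deviation: Anything else". The coverage QA sets per protocol at above 99%, acceptable variation at above 95% and unacceptable deviation at above 90%.

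**Volumes and limits.** Section 9.6 has "GTV: Defined as contrast-enhancing tumor seen on pretreatment MRI", makes the PTV the GTV plus 1 mm on every side, and caps the PTV at 4.0 cm. Sections 3.4 and 7.1 admit a largest lesion of up to 4 cm.

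**The concern.** SIMT SRS is the trial's only intervention, and these sections decide both how it is given and whether its delivery counts as compliant. If they disagree, two planners can treat the same patient differently while each follows the protocol. A plan that obeys the prescribing section can also be scored an unacceptable deviation by the QA section. Deviation counts would then partly measure wording, not delivery. Dose QA has no intermediate tier to absorb such cases. Every patient has at least four treatable metastases (3.4, 7.1), so whether a rule works per lesion or per patient matters whenever sizes are mixed.

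**Working it through.** The protocol states no figure to reproduce here. The inputs are the 9.3 table and sentences, the 9.9 bands and tiers, the 1 mm margin and 4.0 cm cap in 9.6, and the 4 cm limit in 3.4 and 7.1.

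**1. Exactly 3.0 cm.** The middle row of the 9.3 table ends at 3.0 cm and the last row starts at 3 cm, so a 3.0 cm PTV is in both. The 9.3 table (last row) and 9.9 use 3 cm or more for five fractions. The 9.3 summary and 10.3 use more than 3 cm.

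**2. Per lesion or per patient.** Take a patient with one PTV well above 3.0 cm, three well below 2.0 cm, no brainstem lesion, and V12 not above 20 mL. Under the 9.3 table and its per-lesion sentence, one lesion is in the last row and three are in the first. Under 9.9 all four are on the last regimen, so three of the four doses set by 9.3 would be scored as deviations. In 9.3 the explicit all-lesion rule is given for V12 and brainstem only. Its summary can be read as extending that rule to size.

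**3. Exactly 2.0 cm.** The 9.3 table puts a 2.0 cm PTV in the middle row. The eloquent-area sentence puts it with the lesions reduced from 20 Gy, which is the first row, and that sentence's second range also begins at 2 cm.

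**4. Coverage tiers.** As worded, coverage above 99% meets all three conditions, including the unacceptable one. Coverage of 90% or less meets none.

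**5. Doses that 9.3 permits.** The 9.9 Dose QA has no rule for paired lesions and none for decreases on clinical judgment. As an illustration, take PTVs of 10 and 25 mm with a 5 mm gap, assuming that within 1 cm means edge to edge.

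- If the pair is dosed on the larger diameter (25 mm), both are in the middle row.
- If it is dosed on the span (10 + 5 + 25 = 40 mm), both are in the last row.
- Scored singly in 9.9, the smaller lesion is in the first band on either measure (PTV 10 mm, or GTV 10 - 2 = 8 mm).

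**6. Eligibility against the PTV cap.** PTV diameter = GTV diameter + 2 x 1 mm. A cap of 40 mm therefore allows a GTV of at most 40 - 2 = 38 mm. GTVs of 39 and 40 mm give PTVs of 41 and 42 mm, which are eligible by lesion size but over the cap. This assumes that eligibility size is taken before the margin. Section 9.4 supports that: size comes from the planning MRI, and the target is the enhancing part of the lesion.

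**Conditional check: GTV or PTV in 9.9.** I compared 9.3 with 9.9 for whole-millimetre GTVs from 1 to 40 mm. Only four sizes raise a question:

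| GTV (mm) | PTV (mm) | 9.3 (by PTV) | 9.9 if *tumor* is GTV | 9.9 if *tumor* is PTV |
|---|---|---|---|---|
| 18 | 20 | middle (table) or first (eloquent-area sentence) | first | middle |
| 19 | 21 | middle | first | middle |
| 28 | 30 | middle and last | middle | last |
| 29 | 31 | last | middle | last |

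On the GTV reading, 19 and 29 mm clearly differ, and 18 and 28 mm are ambiguous within 9.3. At 29 mm the fractionation differs as well as the dose. In continuous terms the affected GTVs lie between 1.8 and 2.0 cm and between 2.8 and 3.0 cm. On the PTV reading, only the 18 and 28 mm ambiguities remain. Neither difference arises where the brainstem or V12 rule already puts every lesion on one regimen.

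**The case against.** The strongest reply is that 9.9 only restates 9.3 in looser words. Directly after a table headed by PTV diameter, 9.3 itself says "The total prescribed dose is determined by tumor size", so the protocol already uses tumor size for its PTV bands. Section 9.9 repeats the same cut-points and refers back to 9.3. That stands as far as it goes. Section 9.6 ties tumor to GTV, so the term is ambiguous, but the documents do not compel the GTV reading. A reader might infer that tumors between 1.8 and 2.0 cm or between 2.8 and 3.0 cm are certain to be mis-scored. The text does not support that, and the GTV mismatch is therefore secondary here.

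Other replies have partial force:

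- The coverage tiers can be read as a cascade, each applying below the one before. That removes the overlap but still leaves 90% or less without a class.
- Silence in 9.9 on paired lesions need not contradict 9.3, which remains the prescribing rule, and *tumor* might be meant to include a grouped pair. But the catch-all in 9.9 has no exception for doses that 9.3 allows, apart from reductions near critical structures. The numerical pair above depends on how two undefined phrases are read and is only an illustration.
- A planning cap tighter than the eligibility limit is not in itself an error, and 9.3 allows a large lesion to be resected and its cavity treated. What remains is the unresected lesion over 3.8 and up to 4.0 cm.
- Treatment is in one department, so local habit may settle these cases. The protocol does not record how.

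A reader might also infer harm to the primary result. The documents do not show it. Sections 8.4 and 13.1 analyse all treated patients, and no planned analysis uses dose deviations. Section 10.7.1 lists protocol deviation only as a discretionary reason for withdrawal, and nothing equates that with a 9.9 score. Section 10.7.2 keeps withdrawn patients under assessment.

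**Conclusion.** The point holds as an internal inconsistency in the rules for delivering and scoring the only intervention. Items 1 to 4 do not depend on whether *tumor* in 9.9 means GTV or PTV; for item 4, the unclassified range survives even the cascade reading. Item 5 holds as a gap between what 9.3 permits and what 9.9 clearly accepts. Item 6 rests on eligibility size being measured before the margin, and applies to unresected lesions. The GTV/PTV mismatch is conditional: two whole-millimetre sizes clearly differ on one reading and none on the other, with two boundary sizes ambiguous on both.

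These are counts of sizes, not of patients. The documents give no lesion-size distribution, so the share of lesions or patients affected cannot be computed. The consequence shown is inconsistent delivery and deviation scoring. No effect on the survival endpoint or the analysis set is shown, and nothing here says that any patient would receive a wrong dose.

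**What to change.** The sponsor should reconcile 3.4/7.1, 9.3, 9.6, 9.9 and 10.3 so that they state:

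- one size measure for both prescribing and scoring, named as GTV or PTV wherever it is used;
- one handling of exactly 2.0 cm and exactly 3.0 cm, identical in every table, sentence and summary;
- one rule on whether the size trigger acts per lesion or per patient;
- eligibility and PTV size limits that are consistent with each other, saying whether the margin is included;
- in 9.9, how paired lesions and decreases on clinical judgment under 9.3 are scored, so that a dose 9.3 permits is scored consistently with 9.3;
- coverage tiers that are mutually exclusive and cover every value.

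This review takes no position on which dose, measure, cut-off or reduction rule is right; that is for the sponsor and its clinical and physics staff. The cost is a wording amendment. It needs no extra patients, procedures or analyses.
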